7.9 Study Termination

This study may be terminated or suspended at any time. If the study is terminated or suspended, the sponsor will promptly inform the investigators / institutions and PCORI.

Confidential Page **27** of **40** Protocol V7.0 16Feb2022

The IRB should be promptly informed and provided the reasons(s) for the termination or suspension by the sponsor and by the investigator / institution, as specified by the applicable regulatory requirement(s).

8. Safety Monitoring and Reporting

Patients will be closely monitored for adverse events (AEs) or serious adverse events (SAEs), including worsening of depression symptoms. Study investigators will be able to modify treatment or remove patients from the trial based on their clinical discretion and specific patient outcomes.

An adverse event is the development of an undesirable medical condition or the deterioration of a pre-existing medical condition following or during exposure to a pharmaceutical product, whether or not considered causally related to the product. An undesirable medical condition can be symptoms (e.g., nausea, headache, fatigue, blurry vision) or signs (e.g., rapid or irregular heart rate, hypertension). In clinical studies, an AE can include an undesirable medical condition occurring at any time after the informed consent is signed even if no study treatment has been administered.

Assessment of adverse events, including grading of severity and attribution to research will start at the time of consent. AEs will be evaluated at each visit.

For adverse events (AEs), the following guidelines will be used to describe severity.

- **Mild** Events or symptoms that are easily tolerated and do not interfere with the participant's daily activities.
- Moderate Events or symptoms that result in a low to moderate level of inconvenience or concern with normal daily activities. Moderate events may cause some interference with functioning.
- **Severe** Events or symptoms that interrupt a participant's usual daily activity and may require drug therapy or other treatment. Severe events are usually potentially life-threatening or incapacitating. Of note, the term "severe" does not necessarily equate to "serious"

Note: As of 1/1/2018, AEs that are classified as mild, do not need to be reported in the patients chart or the eCRF, per Investigator discretion. AEs classified as moderate or severe, as assessed by an Investigator, need to be reported in the patients chart and the eCRF.

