8.1 Unexpected Adverse Events

The following adverse events will be collected from the time of randomization for the study:

Adverse events that are not listed in the current labeling for ketamine (Ketalar Product Information) or ECT. This includes events that are similar to those on the labeling but differ from the event because of greater severity or specificity.

The following AEs should be captured and recorded on the AE form:

- Prolonged seizure
- Tardive seizure (late occurring)
- Delirium (prolonged)
- Psychosis (prolonged)
- Suicide Attempt
- Severe hypertension (prolonged)
- Dissociation (prolonged)
- Substance abuse (new onset/reoccurrence)
- Clinically significant arrhythmia
- Pregnancy
- Other AEs per Investigator discretion

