8.2 Study Treatment Discontinuation Adverse Events

Events that lead to the discontinuation of either treatment (ECT or ketamine) during the treatment phase, before completion of the final dose, will be collected for the study. These events will be recorded on either an AE or an SAE form.

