Since the QIDS-SR16 score itself is repeatedly measured over time, a linear mixed-effects model will be applied to estimate its trajectories of the two groups during the acute treatment phase. The model will include measurement time, treatment group, their interaction, and site as fixed effects, and a Gaussian random intercept at the patient level. Baseline patient characteristics with statistically significant differences between the two groups may be also included as fixed effects if deemed necessary. The covariance matrix of the repeated measurements within each patient will be selected from the candidates of compound symmetric, first-order autoregressive (AR1), Toeplitz, and unstructured structures using the information criterion. Least-square estimates will be derived to estimate the QIDS-SR16 mean at each visit by group, and corresponding linear contrasts can be used for group comparison at each visit. Since the responders will be further followed at months 1, 3 and 6 after the acute phase, another linear

mixed-effects model with the same formation will be applied to the subgroup of responders for their longitudinal QIDS-SR-16 data until the end of the follow up phase. The model for the change of QIDS-SR-16 score will include the score changes as the dependent variable and further include the baseline QIDS-SR-16 score as a covariate. For the other continuous secondary endpoints measured longitudinally, their analyses will follow the analysis of the QIDS-SR-16 score. These endpoints include various patient and clinician rated scales for depression, suicidality, and cognitive function (e.g., MADRS and YMRS).

For the cross-sectional endpoints such as the MoCA rating assessed at the end of treatment visit, linear regression will be used to analyze and compare the data between the two groups. Generalized linear regression (e.g., logistic regression or ordinal logistic regression) will be applied to binary or multi-categorical outcomes, depending on the variable type of the outcome.

Analysis of safety endpoints. Mortality will be summarized as percentage by group, and the chi-squared test will be used to compare the mortality rates between the two groups. If the expected number of deaths is small, the Fisher's exact test will be used instead. The other dichotomous safety outcomes such as the unexpected adverse events, adverse events causing treatment discontinuation and serious adverse events will be analyzed in the same manner.

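### The Section 8 Note makes recording of mild AEs optional without excepting 8.1 or 8.2 events, so two SAP safety endpoints may be undercounted, possibly unequally by arm

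*Protocol*

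**What the plan says.** **Protocol, Section 8, Note (effective 1/1/2018).** "AEs that are classified as mild, do not need to be reported in the patients chart or the eCRF, per Investigator discretion". For the other grades the rule is mandatory: "AEs classified as moderate or severe, as assessed by an Investigator, need to be reported in the patients chart and the eCRF". Mild is defined earlier in the same section as "Events or symptoms that are easily tolerated and do not interfere with the participant's daily activities".

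**Protocol, Section 8.1.** "The following adverse events will be collected from the time of randomization for the study". The first class is "Adverse events that are not listed in the current labeling for ketamine (Ketalar Product Information) or ECT". A named list follows under the instruction "The following AEs should be captured and recorded on the AE form".

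**Protocol, Section 8.2.** Events that lead to either treatment being discontinued "before completion of the final dose, will be collected for the study. These events will be recorded on either an AE or an SAE form".

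**SAP, Analysis of safety endpoints.** After setting out a chi-squared or Fisher's exact comparison for mortality, the SAP extends that approach to the AE endpoints: "The other dichotomous safety outcomes such as the unexpected adverse events, adverse events causing treatment discontinuation and serious adverse events will be analyzed in the" (quotation cut short here). SAP Table 1 lists both AE endpoints by name only, with no severity limit and no date rule.

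**Blinding.** Protocol Section 5.4 states that neither patient nor clinician can be blinded to arm.

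**The concern.** The Note classifies events by grade. Section 8.1 classifies them by whether they are in the labeling or on a list, and 8.2 by whether treatment stopped. These classifications overlap. An AE that is mild and not in the labeling is to be collected under 8.1 and optional under the Note. The same holds for a mild AE that leads to stopping under 8.2. Sites could reasonably resolve this differently.

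Two features make it matter for the analysis. First, the person who assigns the grade and holds the discretion to record knows the treatment, so omission can depend on arm. Second, the Note covers the chart as well as the eCRF, so an omitted event may leave no source record for monitoring to find. At stake is whether two between-arm safety percentages can be interpreted, in a trial whose rationale (Protocol Section 2) gives weight to the side effects of ECT.

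**Working it through.** The documents state no AE rate or AE power, so there is no plan figure to reproduce. The check is mainly one of text, followed by an illustration.

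**1. The rules side by side**

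| Source | Events covered | Severity limit | Recording |
|---|---|---|---|
| Section 8 Note | every AE graded mild | mild only | optional |
| Section 8 Note | every AE graded moderate or severe | moderate or severe | mandatory |
| 8.1 | AEs not in the labeling; named list | none | to be collected; listed events go on the AE form |
| 8.2 | AEs leading to discontinuation | none | to be recorded on an AE or SAE form |
| SAP safety section and Table 1 | both classes | none | compared between arms |

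No text gives an order of precedence.

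**2. Which events are exposed**

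- Mild AEs absent from the labeling: fully exposed.
- Named 8.1 events: mostly not, since events such as severe prolonged hypertension or suicide attempt would rarely be graded mild. Suicide attempt is also given as an SAE example in the synopsis, and pregnancy has its own rule in 8.5. Some, such as prolonged dissociation, could be.
- Mild AEs leading to discontinuation: possible, but an easily tolerated event should seldom end treatment.
- SAEs: not exposed, as 8.3 has its own collection rule.

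**3. The date**

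The effective date suggests that the rule changed, but the documents give no enrolment start. If patients were observed before 1/1/2018, ascertainment may differ across that date. The definitions in 8.1, 8.2 and SAP Table 1 carry no date.

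**4. Illustration (all rates assumed)**

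Let p be the true proportion of patients with a qualifying event, m the share of those patients whose qualifying events are all mild, and q the share of such patients left unrecorded. Then

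observed rate = p × (1 − m × q).

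*Equal omission in both arms.* The undercount is m × q. With m from 10% to 50% and q from 50% to 100%, it runs from 0.10 × 0.50 = 5% to 0.50 × 1.00 = 50%. The risk ratio stays 1.00 under no true difference and the test keeps its 5% size. Absolute rates, and any true risk difference, shrink by the same fraction.

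*Unequal omission, no true difference.* Take q = 25% in one arm and 75% in the other, so the observed risk ratio is (1 − 0.75m) / (1 − 0.25m). Write d for the observed difference, se0 for its pooled standard error and se1 for its unpooled standard error. With the planned 200 per arm and a two-sided 5% pooled z test (equivalent to the chi-squared test), the false-positive rate is Φ((d − 1.96·se0)/se1) + Φ((−d − 1.96·se0)/se1).

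Example, p = 20% and m = 30%:
- observed rates 0.20 × (1 − 0.075) = 18.5% and 0.20 × (1 − 0.225) = 15.5%, so d = 0.030
- se0 = √(2 × 0.17 × 0.83 / 200) = 0.0376
- se1 = √((0.185 × 0.815 + 0.155 × 0.845) / 200) = 0.0375
- false-positive rate 12.5%

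| m | Observed risk ratio | False-positive rate, p = 10% | False-positive rate, p = 20% |
|---|---|---|---|
| 10% | 0.95 | 5.3% | 5.7% |
| 30% | 0.84 | 8.4% | 12.5% |
| 50% | 0.71 | 15.8% | 28.8% |

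Given step 2, the low-m row is the more plausible one for discontinuation AEs. For unlabeled AEs the documents offer no guide to m.

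**The case against.** The strongest reply is that specific rules control general ones. Sections 8.1 and 8.2 are specific and directive, the Note is general and only permissive, and a site may well read 8.1 and 8.2 as overriding it. That reading is reasonable, but the documents do not state it.

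A second reply is that the grading scale does most of the work. A patient who gives up treatment over a complaint has hardly tolerated it easily, and moderate already begins at a low level of inconvenience, so such an event would normally be moderate and mandatory. This stands, and it is why 8.2 is the lesser exposure. It does not help with mild unlabeled events.

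Third, side effects are also captured elsewhere. PRISE, SMCQ and GSE-My are patient-rated and scheduled in both arms regardless of AE grade. They soften the concern about tolerability in general, but they are separate endpoints and do not restore the AE-form counts.

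A reader might infer that the two endpoints are in fact undercounted, or that their definitions change on 1/1/2018. The documents support neither. Omission is permitted but not shown, and only ascertainment could shift at that date, and only if patients were observed before it.

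**Conclusion.** The conflict is real and narrow. As written, the Note lets an unblinded investigator leave out mild events that 8.1 and 8.2 say will be collected, and the SAP compares both classes between arms without stating what grades count. The two percentages may be understated, and the comparison may be biased if omission differs by arm. With equal omission, a comparison under no true difference is not biased.

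The size cannot be derived from the documents. The figures above depend on assumed event rates, mild shares and omission rates; with few mild cases among qualifying events the effect is slight. The primary endpoint, the non-inferiority margin and the sample size are not affected. The point is worth correcting because otherwise readers cannot tell what the two reported percentages count.

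**What to change.** - **Protocol, Section 8 Note.** Reconcile the passages by adding that the exemption does not apply to any event under 8.1, whether unlabeled or listed, or under 8.2, and that these are recorded on the AE or SAE form whatever their grade.
- **SAP, unexpected AEs.** SAP version 2.0 was drafted at the end of the study, so a protocol sentence cannot recover events already omitted. Base the between-arm comparison on moderate or severe events, whose recording the Note makes mandatory, and report recorded mild events descriptively, including any from the 8.1 list. This gives one recording rule on both sides of 1/1/2018. It removes the discretion to record, though grading itself remains unblinded.
- **SAP, discontinuation AEs.** Report at any grade, and cross-check against the recorded reason for stopping where there is one. This is only a cross-check: Section 7.7 says the investigator should ask the reason when the subject elects to stop, does not say that the answer is recorded, and does not cover treatment ended by the investigator under 7.3.3.

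Cost: one sentence in the protocol, a few in the SAP, a few extra AE forms, and a somewhat lower unexpected-AE percentage.

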8.1 Unexpected Adverse Events

The following adverse events will be collected from the time of randomization for the study:

Adverse events that are not listed in the current labeling for ketamine (Ketalar Product Information) or ECT. This includes events that are similar to those on the labeling but differ from the event because of greater severity or specificity.

The following AEs should be captured and recorded on the AE form:

- Prolonged seizure
- Tardive seizure (late occurring)
- Delirium (prolonged)
- Psychosis (prolonged)
- Suicide Attempt
- Severe hypertension (prolonged)
- Dissociation (prolonged)
- Substance abuse (new onset/reoccurrence)
- Clinically significant arrhythmia
- Pregnancy
- Other AEs per Investigator discretion

8.2 Study Treatment Discontinuation Adverse Events

Events that lead to the discontinuation of either treatment (ECT or ketamine) during the treatment phase, before completion of the final dose, will be collected for the study. These events will be recorded on either an AE or an SAE form.

8.3 Serious Adverse Events

All SAEs that meet the following definition will be collected from the time of consent until completion of either the One Month Follow-Up Call (for non-responders) or throughout the applicable follow-up visit (for responders).

- Results in death
- Is immediately life-threatening
- Requires in-patient hospitalization or prolongation of existing hospitalization
- Results in persistent or significant disability/incapacity or substantial disruption of the ability to conduct normal life functions
- Is a congenital abnormality or birth defect
- Is an important medical event that may jeopardize the patient or may require medical intervention to prevent one of the outcomes listed above

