All patients will complete self-reported cognitive assessments, depression questionnaires, and quality of life scales at the Baseline Visit/Visit 1 and throughout the acute treatment phase of the study (see Schedule of Events). Diagnostic interviews and clinician rated scales will also be performed at regular intervals throughout the acute treatment phase.

After the acute treatment phase, all patients will complete an EOT visit within 3 days of their last study treatment and will be classified as either a responder or a nonresponder. Patients may continue to receive ECT or ketamine clinically after the EOT visit, but this will mark the end of the acute treatment phase of the study. If the patient is a responder, any ECT or ketamine treatments administered after the EOT visit will be recorded in the follow-up phase. If the patient is not a responder they will receive a phone call one month after the End of Treatment Visit for completion of PGI-I, PGI-S, QIDS and MADRS, and record any ECT or ketamine treatments administered after the EOT visit. This will conclude their participation in the study and they will be

Confidential Page **13** of **40** Protocol V7.0 16Feb2022 treated clinically.

Responder: a patient who achieves a \geq 50% decrease in their QIDS-SR-16 score from Baseline/Visit 1 to the End of Treatment visits. Responders may continue in the study for three follow-up visits at one month, three months, and six months after the EOT Visit, depending on the date of enrollment relative to the end of study. They will continue naturalistic treatment with a clinician of their choice.

Non-Responder: a patient who achieves <50% decrease in their QIDS-SR-16 score from Baseline/Visit 1 to the End of Treatment Visit. Non-responders will receive a phone call at one month after the EOT Visit. They will be exited from the study after the one month phone follow-up visit and will not be contacted or seen for the three and six month follow-up visits. They will continue treatment with the clinician of their choice.

Early Completion of Acute Treatment Phase

The investigator or patient can choose to stop treatment at any time. Investigators will monitor patients closely for signs of improvement, remission, or decline. The investigator will use his or her discretion and clinical judgment to determine if a patient should stop treatment and be scheduled for an End of Treatment Visit.

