5.1 Recruitment of Trial Participants

Inpatients or Outpatients with TRD without psychotic features referred by their clinical providers for ECT, and found to be eligible for ECT treatment, will be pre-screened for the study. Potential patients will be approached after a psychiatrist has evaluated them and recommended them for clinical ECT treatment. At this time, the patient will be informed about the study and given a thorough explanation of risks, benefits, study procedures, and expectations.

Patients interested in participation will be scheduled for a screening visit as soon as possible, but no later than 28 days from the clinical consult. Typically patients should be

Confidential Page **15** of **40** Protocol V7.0 16Feb2022

scheduled for screening within two weeks from the consult.

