7.4 End of Treatment (EOT) Visit

Patients should complete an EOT visit within three (3) days of their last study treatment. If patients do not stop treatment early, this will occur after the 9th ECT treatment or the 6th ketamine treatment. If patients stop earlier, the EOT visit should occur within three (3) days of this final treatment. Patients may continue to receive ECT or ketamine clinically, but the EOT visit marks the end of the acute treatment phase for the study.

- Vitals (BP, Heart rate)
- Update Medical History
- Update Psychiatric Medication Log
- Update Somatic Therapies Log
- Evaluation for AEs or SAEs
- Clinical Psychiatric Evaluation
- Patient Rated Behavioral Scales
 - QIDS-SR-16 (to be completed first)
 - o GSE-MY
 - o SMCQ
 - o PGI-S & PGI-I
 - o QOLS
 - o PRISE
 - o CPFQ
 - Treatment Preference Questionnaire
- Clinician Rated Behavioral Scales
 - MADRS
 - o CSSRS
 - o YMRS
 - o BPRS
 - o CGI-S & CGI-I
 - CADSS
- Cognitive Assessments
 - o MoCA
 - o COWAT
 - o HVLT-R
 - Stroop

Patients will be classified as responders or non-responders after the EOT Visit.

Responders will be patients who had a \geq 50% decrease in their QIDS-SR-16 score from Baseline/Visit 1 to the EOT Visit. Responders will be asked to participate in the follow-up

phase of the study. Follow-up visits may occur one month, three months, and six months after the EOT Visit, depending on the date of enrollment relative to the end of study.

Non-responders will have had < 50% decrease in their QIDS-SR-16 score from Baseline/Visit 1 to the EOT Visit. Non-responders will not be seen for follow-up visits. However, these patients will receive a follow-up phone call one month after the End of Treatment Visit.

Inpatient / Outpatient Status - If the patient was an inpatient at randomization, record if they were discharged during treatment and the date of discharge, at the End of Treatment Visit.

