7.5.2 Follow-Up Phone Call for Non-Responders

7.5.2.1 Month 1 Follow-Up Phone Call (+/- 2 weeks)

- Evaluation for Adverse Events or Serious Adverse Events
- Evaluation for additional ECT, ketamine, psychotropic treatment(s) performed
 - o Update Somatic Therapies Log
 - Update Psychiatric Medications Log
- Patient Rated Behavioral Scale
- PGI-S & PGI-I
- Completion of QIDS
- Completion of MADRS

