8.4 Documentation and Reporting of Serious Adverse Events

SAEs will be reported to C5Research within 24 hours of learning of the event. The causality of the SAE (the relationship to the study treatment/procedures) will be assessed by the investigator. The SAE will also be documented on the appropriate eCRF.

Since the use of Ketamine in the ELEKT-D study is exempted from IND reporting, the Investigator does not have the responsibility to report any AEs/SAEs to the FDA.

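### The SAP compares serious and unexpected adverse events by group with no split at End of Treatment, so study-course harms are mixed with events after later clinical ECT or ketamine and with follow-up that depends on response

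*Protocol*

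**What the plan says.** - **Collection period.** Protocol section 8.3: "All SAEs that meet the following definition will be collected from the time of consent until completion of either the One Month Follow-Up Call". That call is where collection ends in non-responders; in responders it runs to the last applicable follow-up visit, which can be Month 6. Section 8.1 starts collection of unexpected adverse events at randomisation and states no end. Adverse events are also reviewed at the responders' visits and at the non-responders' Month 1 call (section 7.5).
- **Treatment after EOT.** Section 7.4: "Patients may continue to receive ECT or ketamine clinically, but the EOT visit marks the end of the acute treatment phase". Section 3 says the same and sets no bar on receiving the treatment that was not assigned.
- **Recording.** For responders, "any ECT or ketamine treatments administered after the EOT visit will be recorded in the follow-up phase" (section 3). For non-responders, the Month 1 call includes "Evaluation for additional ECT, ketamine, psychotropic treatment(s) performed" (section 7.5.2.1), with an update of the Somatic Therapies Log.
- **Population.** Section 5.1: "Potential patients will be approached after a psychiatrist has evaluated them and recommended them for clinical ECT treatment".
- **Causality.** Section 8.4: "The causality of the SAE (the relationship to the study treatment/procedures) will be assessed by the investigator".
- **Analysis.** The SAP's safety section takes "The other dichotomous safety outcomes such as the unexpected adverse events, adverse events causing treatment discontinuation and serious adverse events" and handles them as it handles mortality: a percentage by group, with a chi-squared or Fisher test. It names no time window, no safety population and no analysis by treatment received.
- **Follow-up scales.** The SAP models responders' longitudinal scores with time, group, their interaction and site. There is no term for treatment after EOT. Protocol section 4.2 makes EOT the baseline for follow-up.

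**The concern.** The trial tests whether ketamine is non-inferior to ECT on response. If it is, the comparison of harms will weigh heavily in choosing between them, and a reader will want to know what the assigned course of treatment did. One percentage per arm over the whole collection period does not answer that, for two reasons.

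First, it includes events that follow later clinical treatment. All participants had been recommended for ECT before entry, so ECT after an unsuccessful ketamine course is plausible. An event that it caused would be counted in the ketamine arm. Later ketamine in an ECT-arm patient is counted in the ECT arm in the same way.

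Second, a responder can be observed for up to six months after EOT and a non-responder for about one. The arm with more responders is therefore watched longer on average, and raw percentages do not allow for this.

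The information needed to separate these components is collected, but no planned analysis uses it.

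**Working it through.** No stated figure is in dispute, so the check sets the provisions against each other and then sizes the two effects.

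**1. Which outcomes are exposed**

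| Outcome | Collected after EOT? | Exposed? |
|---|---|---|
| Serious adverse events | Yes, 1 month or up to 6 months by response (8.3) | Yes |
| Unexpected adverse events | No end stated (8.1) | Yes |
| Discontinuation adverse events | No, treatment phase only (8.2) | No |
| Memory and cognition up to EOT | No | No |
| Memory and cognition, Months 1, 3 and 6 | Responders only; the non-responder call has PGI, QIDS and MADRS | Responders only |

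**2. Patients at risk.** The synopsis expects 60% responders: 0.60 × 400 = 240, or 120 per arm, which leaves 200 − 120 = 80 non-responders per arm.

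**3. Events added by later non-assigned treatment.** Added events = patients at risk × share treated × attributable risk. The documents give neither of the last two. I assume shares of 10–50% and risks of 2–10%, with at most one event per patient.
- Ketamine-arm non-responders, low: 80 × 0.10 × 0.02 = 0.16 events; 0.16/200 = 0.08 percentage points.
- High: 80 × 0.50 × 0.10 = 4.0 events; 4.0/200 = 2.0 points.
- Same shares and risks across all 200 ketamine-arm patients: 0.4 to 10 events, or 0.2 to 5.0 points.

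**4. Direction.** Later ketamine in ECT-arm non-responders adds events to the ECT arm by the same formula. With the same assumed ranges in both arms, the net shift in the ECT-minus-ketamine difference runs from (0.16 − 4.0)/200 = −1.92 points to (4.0 − 0.16)/200 = +1.92 points. The range straddles zero, so the sign is not determined.

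**5. Unequal follow-up.** With response rate r, one month for non-responders and the full six for responders, mean scheduled observation after EOT is 1 × (1 − r) + 6 × r = 1 + 5r months. The SAP's sample size section assumes 50% for ECT: 1 + 5 × 0.50 = 3.5 months. For ketamine:
- true difference +5 points: 1 + 5 × 0.55 = 3.75 months, ratio 3.75/3.5 = 1.07;
- +10 points: 1 + 5 × 0.60 = 4.0 months, ratio 1.14;
- −10 points, at the margin: 1 + 5 × 0.40 = 3.0 months, ratio 0.86.

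These are upper limits on the imbalance. Month 3 and Month 6 visits depend on the enrolment date, and the synopsis expects 192 of 240 responders to complete follow-up. If every responder stopped at Month 1, the imbalance would vanish.

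**6. Follow-up memory scores.** If 10–50% of ketamine-arm responders later had ECT, with an assumed effect of 0.3–0.8 SD, the arm mean would shift by 0.10 × 0.3 = 0.03 to 0.50 × 0.8 = 0.40 SD. Both inputs are assumptions, and responders have less evident reason to change treatment.

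**The case against.** A comparison by randomised arm is the standard, unconfounded way to report harms. It answers a treatment-policy question and accords with the intention-to-treat statement in protocol section 9. Later suicide attempts and relapse hospitalisations may be consequences of the first treatment, and a table that stops at EOT, which is due within three days of the last treatment, would miss them. Investigator causality assessment can help to separate later clinical treatment. The protocol speaks of patients continuing ECT or ketamine, and continued assigned treatment is not misattributed. All of this stands, and it is why the all-events table should stay. It does not close the gap: the SAP does not say that a treatment-policy comparison is intended, does not use the causality assessment, and gives no view of the acute course alone.

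A reader might infer that the plan systematically charges ECT harms to ketamine and shrinks a true difference. The documents do not support a direction. Later ketamine in the ECT arm adds events there and would offset the effect, and no rate of switching is given. Nor do they support a specific loss of power, which would follow entirely from the event risks one chose to assume. A reader might also infer that the memory comparison in Aim 2 is compromised. It is not at EOT, and non-responders, the likelier switchers, have no memory or cognitive scale afterwards.

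**Conclusion.** The concern holds as a gap in the safety analysis. As written, the percentages of serious and unexpected adverse events mix three things: harms of the study course, events after later and possibly non-assigned treatment, and follow-up whose length depends on each arm's response rate. Taking group to mean randomised arm, and the period to be the whole collection window, is a reading of the SAP's silence: it defines neither a safety population nor a window.

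Under the assumptions shown, later ECT among ketamine-arm non-responders adds 0.08 to 2.0 percentage points, with an opposing contribution possible in the ECT arm. Mean post-EOT observation could differ between arms by anything from nothing to about 14% if response rates differ by up to 10 points. The true size and net direction cannot be known from the documents. Discontinuation events and memory and cognition up to EOT are unaffected; follow-up memory scores are affected in responders only.

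**What to change.** In the SAP safety section:

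1. Keep the table of all events by randomised arm, and state its window and that it is a treatment-policy summary.
2. Add a by-arm comparison of serious and unexpected adverse events with onset from first study treatment to the EOT visit. For patients without an EOT visit, end the window at the close of the protocol's own three-day EOT window after the last study treatment. Events before first study treatment stay in the all-events table.
3. Tabulate post-EOT events separately by arm and responder status, and by whether ECT or ketamine was received after EOT and before onset, using the Somatic Therapies Log. Label this table descriptive and non-randomised.
4. For follow-up memory and cognitive scales, report by arm how many responders received ECT or ketamine after EOT. Do not drop visits after a switch, because that conditions on a post-randomisation event probably related to outcome.

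The cost is SAP wording and a few tables from data already collected, provided that event onset and later treatments are dated; the documents do not show the forms. The acute-phase table will hold fewer events, and late harms will appear only in the all-events and post-EOT tables.
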